#### **7.4. Gilead Reporting Requirements**

Depending on relevant local legislation or regulations, including the applicable US FDA Code of Federal Regulations, the EU Clinical Trials Directive (2001/20/EC) and relevant updates, and other country-specific legislation or regulations, Gilead may be required to expedite to worldwide regulatory agencies reports of SAEs, serious adverse drug reactions (SADRs), or suspected unexpected serious adverse reactions (SUSARs). In accordance with the

EU Clinical Trials Directive (2001/20/EC), Gilead or a specified designee will notify worldwide regulatory agencies and the relevant IEC in concerned Member States of applicable SUSARs as outlined in current regulations.

Assessment of expectedness for SAEs will be determined by Gilead using reference safety information specified in the investigator's brochure or relevant local label as applicable.

All investigators will receive a safety letter notifying them of relevant SUSAR reports associated with any study IMP. The investigator should notify the IRB or IEC of SUSAR reports as soon as is practical, where this is required by local regulatory agencies, and in accordance with the local institutional policy.

### **7.5. Clinical Laboratory Abnormalities and Other Abnormal Assessments as Adverse Events or Serious Adverse Events**

Laboratory abnormalities without clinical significance are not recorded as AEs or SAEs. However, laboratory abnormalities (eg, clinical chemistry, hematology, and urinalysis) that require medical or surgical intervention or lead to ENTO interruption, modification, or discontinuation must be recorded as an AE, as well as an SAE, if applicable. In addition, laboratory or other abnormal assessments (eg, electrocardiogram, x-rays, vital signs) that are associated with signs and/or symptoms must be recorded as an AE or SAE if they meet the definition of an AE or SAE as described in Section 7.1. If the laboratory abnormality is part of a syndrome, record the syndrome or diagnosis (eg, anemia), not the laboratory result (ie, decreased hemoglobin).

### **7.6. Toxicity Management**

It is recognized that drug-related toxicity in this population may be difficult to ascertain given the aggressive hematologic disease. Investigators will attempt to assign attribution of toxicities to each drug if possible. The CTEP Active Version of the NCI Common Terminology Criteria for Adverse Events (CTCAE) version 4.03 will be utilized for AE reporting. See Section 8.6.2.

### **7.7. Special Situations Reports**

#### **7.7.1. Definitions of Special Situations**

Special situation reports include all reports of medication error, abuse, misuse, overdose, reports of AEs associated with product complaints, and pregnancy reports regardless of an associated AE.

Medication error is any unintentional error in the prescribing, dispensing, or administration of a medicinal product while in the control of the health care provider, subject, or consumer.

Abuse is defined as persistent or sporadic intentional excessive use of a medicinal product by a subject.

Misuse is defined as any intentional and inappropriate use of a medicinal product that is not in accordance with the protocol instructions or the local prescribing information.

An overdose is defined as an accidental or intentional administration of a quantity of a medicinal product given per administration or cumulatively which is above the maximum recommended dose as per protocol or in the product labelling (as it applies to the daily dose of the subject in question). In cases of a discrepancy in drug accountability, overdose will be established only when it is clear that the subject has taken the excess dose(s). Overdose cannot be established when the subject cannot account for the discrepancy except in cases in which the investigator has reason to suspect that the subject has taken the additional dose(s).

Product complaint is defined as complaints arising from potential deviations in the manufacture, packaging, or distribution of the medicinal product.

### **7.7.2. Instructions for Reporting Special Situations**

The investigator should report pregnancies in female study subjects that are identified after initiation of study medication and throughout the study, including the post study drug follow-up period, to Gilead DSPH (Fax: PPD or email: PPD) using the pregnancy report form within 24 hours of becoming aware of the pregnancy.

Refer to the eCRF completion guidelines for full instructions on the mechanism of pregnancy reporting.

The pregnancy itself is not considered an AE nor is an induced elective abortion to terminate a pregnancy without medical reasons.

Any premature termination of pregnancy (eg, a spontaneous abortion, an induced therapeutic abortion due to complications or other medical reasons) must be reported within 24 hours as an SAE. The underlying medical reason for this procedure should be recorded as the AE term.

A spontaneous abortion is always considered to be an SAE and will be reported as described in Section 7.3. Furthermore, any SAE occurring as an adverse pregnancy outcome post study must be reported to Gilead DSPH.

The subject should receive appropriate monitoring and care until the conclusion of the pregnancy. The outcome should be reported to Gilead DSPH using the pregnancy outcome report form. If the end of the pregnancy occurs after the study has been completed, the outcome should be reported directly to Gilead DSPH. Gilead DSPH contact information is as follows:  
Email: PPD and Fax: PPD

Pregnancies of female partners of male study subjects exposed to Gilead or other study drugs must also be reported and relevant information should be submitted to or Gilead DSPH using the pregnancy and pregnancy outcome forms within 24 hours. Monitoring of the subject should continue until the conclusion of the pregnancy. If the end of the pregnancy occurs after the study has been completed, the outcome should be reported directly to Gilead DSPH. Fax number: PPD or email: PPD

Refer to [Appendix 4](#) for Pregnancy Precautions, Definition for Female of Childbearing Potential, and Contraceptive Requirements.

### **7.7.3. Reporting Other Special Situations**

All other special situation reports must be reported on the special situations report form and forwarded to Gilead DSPH within 24 hours of the investigator becoming aware of the situation. These reports must consist of situations that involve study IMP and/or Gilead concomitant medications, but do not apply to non-Gilead concomitant medications.

Special situations involving non-Gilead concomitant medications does not need to be reported on the special situations report form; however, for special situations that result in AEs due to a non-Gilead concomitant medication, the AE should be reported on the AE form.

Any inappropriate use of concomitant medications prohibited by this protocol should not be reported as “misuse,” but may be more appropriately documented as a protocol deviation.

Refer to Section 7.7 and the eCRF completion guidelines for full instructions on the mechanism of special situations reporting.

All clinical sequelae in relation to these special situation reports will be reported as AEs or SAEs at the same time using the AE eCRF and/or the SAE report form. Details of the symptoms and signs, clinical management, and outcome will be reported, when available.

## **8. STATISTICAL CONSIDERATIONS**

### **8.1. Analysis Objectives and Endpoints**

#### **8.1.1. Analysis Objectives**

[figure not shown]
The primary objectives of this study are:

- To evaluate the safety and tolerability of ENTO monotherapy in Japanese subjects with relapsed or refractory hematologic malignancies
- To evaluate the safety and tolerability of ENTO in combination with cytarabine and daunorubicin (7+3) in Japanese subjects with previously untreated AML who are candidates for chemotherapy

The secondary objectives of this study are:

- To evaluate the PK of ENTO in Japanese subjects with relapsed or refractory hematologic malignancies
- To evaluate the PK of ENTO in Japanese subjects with previously untreated AML who are candidates for chemotherapy
- To evaluate the safety and tolerability of ENTO in combination with age-adjusted HiDAC in Japanese subjects with previously untreated AML who are candidates for chemotherapy

The exploratory objectives of this study are:

#### **8.1.2. Primary Endpoints**

The primary endpoints of this study are:

Safety Endpoints:

- Occurrence of AEs and laboratory abnormalities defined as DLTs for ENTO monotherapy in subjects with relapsed or refractory hematologic malignancies
- Occurrence of AEs and laboratory abnormalities defined as DLTs for ENTO in combination with cytarabine and daunorubicin in subjects with previously untreated AML who are candidates for chemotherapy

### **8.1.3. Secondary Endpoints**

The secondary endpoints of this study are:

Safety

- Occurrence of AEs, laboratory findings and findings on physical exam not defined as DLTs

Pharmacokinetics

- Determination of the PK parameters of ENTO based on plasma concentrations

### **8.1.4. Other Endpoints of Interest**

The exploratory endpoints of this study are:

## **8.2. Analysis Conventions**

### **8.2.1. Analysis Sets**

#### **8.2.1.1. Full-Analysis Set (FAS)**

Full-Analysis Set (FAS) includes all subjects who receive at least 1 dose of study drug (ENTO). This analysis set will be used in the analyses of subject characteristic, drug exposure, safety, and efficacy.

#### **8.2.1.2. DLT Analysis Set**

DLT Analysis Set includes all subjects in FAS who receive sufficient drug exposure (Section 3.2) or experience a DLT during the DLT assessment window.

#### **8.2.1.3. Pharmacokinetic Analysis Sets**

Pharmacokinetic Analysis Sets include all subjects in FAS who have necessary baseline and post-treatment assessments in order to provide interpretable results for the specific parameters of interest.

## **8.3. Data Handling Conventions**

By-subject listings will be created for important variables from each eCRF module. Summary tables for continuous variables will contain the following statistics: N (the number of subject in group), n (the number of subjects with assessment), mean, standard deviation, 95% confidence intervals (CIs) on the mean, median, minimum, and maximum. Summary tables for categorical variables will include: N, n, percentage, and 95% CIs on the percentage. Unless otherwise indicated, 95% CIs for binary variables will be calculated using the binomial distribution (exact method) and will be 2-sided. Data will be described and summarized by dose level, analysis set, and timepoint. As appropriate, changes from baseline to each subsequent timepoint will be described and summarized. Similarly, as appropriate, the best change from baseline during the study will also be described and summarized. Graphical techniques (eg, waterfall plots, Kaplan-Meier curves, line plots) may be used when such methods are appropriate and informative.

The baseline value used in each analysis will be the last (most recent) pre-treatment value. Data from all sites will be pooled for all analyses. Analyses will be based upon the observed data unless methods for handling missing data are specified. If there is a significant degree of non-normality, analyses may be performed on log-transformed data or nonparametric tests may be applied, as appropriate.

Unless otherwise specified, all analyses will be 2-sided at the 0.05 level of significance.

#### **8.4. Demographic Data and Baseline Characteristics**

A listing of all full-analysis subjects will be generated to describe site, subject number, first screening date, first treatment date, dose level, duration of study treatment, reasons of study treatment discontinuation, and reasons of study discontinuation. Available information on subjects who are screened but are not treated may be listed separately.

Subject demographic and baseline characteristics will be listed and summarized by dose level based on Full Analysis set.

#### **8.5. Efficacy Analysis**

Assessment of clinical response in subjects with hematologic malignancies other than AML will be according to the latest set of published response criteria. Assessment of clinical response in subjects with AML will be according to the modified International Working Group criteria and will include findings on examination of blood, bone marrow and physical examination.

Complete Remission Rate and Composite Complete Remission Rate and other response rate variables will be described. In the analyses of Complete Remission Rate and Composite Complete Remission Rate by induction completion, subjects who do not have evaluable post-treatment assessment to characterize response will be counted as non-responder. For all analyses, the corresponding 95% exact CIs will be presented.

#### **Time-to-Event Endpoints**

RFS, EFS and OS will be analyzed using Kaplan-Meier (KM) methods. The KM estimate of the survival function will be computed and the results will be presented using KM curves. The median will be provided along with the corresponding 95% CI. Additionally, the 25% and 75% percentiles for these endpoints will also be provided. In addition, the estimated rate at 6-month, 12-month, 2-year, and 3-year will be reported.

The following censoring rules will be applied:

RFS: For subjects who are not known to have relapsed or died by the end of the study or data cutoff, RFS is censored on the date of the last available disease assessment.

EFS: For subjects with none of the events defined in EFS before the end of the study or data cutoff, EFS is censored at the date of the last available disease assessment.

OS: For subjects who are not known to have died by the end of the study or data cutoff, OS is censored on the last dates on which the subjects are known to be alive.

Analysis of Complete Remission Duration and Composite Complete Remission Duration will be analyzed using cumulative incidence by considering death without relapse as competing risks. The estimate of the cumulative incidence of relapse (CIR) will be reported with the associated

95% CI. For subjects who die without report of relapse, Complete Remission Duration and Composite Complete Remission Duration are censored on the date of death, regardless of cause. For subjects with no report of relapse by the end of the study or data cutoff date, the Remissions are censored on the date of the last available disease assessment.

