## 1. INTRODUCTION

This statistical analysis plan (SAP) describes the statistical analysis methods and data presentations to be used in tables, figures, and listings (TFLs) in a synoptic study report (CSR) for Study GS-US-429-4104. This SAP is based on Protocol GS-US-429-4104 Amendment 3 dated 23 August 2017 and the electronic case report form (eCRF). The SAP will be finalized before database finalization. Any changes made after the finalization of the SAP will be documented in the CSR.

The study was originally designed to evaluate the safety, tolerability, and pharmacokinetics of entospletinib (ENTO) in 2 stages: (1) ENTO monotherapy (Group A) for relapsed or refractory hematologic malignancies; (2) ENTO in combination with cytarabine and daunorubicin (Group B) for AML. However, per the Sponsor's decision, only the monotherapy stage is conducted with full enrollment of Group A, and the study will be terminated early without opening enrollment in Group B. The decision to terminate the study was not due to any safety concerns. Therefore, a synoptic CSR will be generated, and this SAP describes the analyses for the monotherapy part (Group A) only.

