### **3. GENERAL CONSIDERATIONS FOR DATA ANALYSES**

As the study was terminated early with only 9 subjects enrolled, the synoptic CSR will only include listings for efficacy analyses. Both summarized tables and listings will be provided for safety analyses.

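### Does censoring deaths in remission turn the protocol's cumulative incidence of relapse into 1 minus Kaplan-Meier?

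*Protocol*

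**What the plan says.** The relevant text is the last paragraph under Time-to-Event Endpoints in Protocol Section 8.5.

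- **Method.** Complete Remission Duration and Composite Complete Remission Duration "will be analyzed using cumulative incidence by considering death without relapse as competing risks".
- **Reported quantity.** "The estimate of the cumulative incidence of relapse (CIR) will be reported with the associated" 95% CI.
- **Death in remission.** "For subjects who die without report of relapse, Complete Remission Duration and Composite Complete Remission Duration are censored on the date of death", whatever the cause of death.
- **No relapse reported by study end or data cutoff.** "the Remissions are censored on the date of the last available disease assessment".

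The SAP sets what will be produced. Section 1 explains that Group B was never opened and that "this SAP describes the analyses for the monotherapy part (Group A) only". Section 3 adds: "As the study was terminated early with only 9 subjects enrolled, the synoptic CSR will only include listings for efficacy analyses".

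The exploratory endpoint lists in the protocol (Synopsis, Sections 3.1 and 8.1.4) and SAP Sections 6.3.1 to 6.3.3 are blacked out or blank in the public copies. Remission duration is not among the primary or secondary endpoints, so its definition would be expected in those places.

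**The concern.** In one estimator a death cannot be both a competing event and a censored observation. The protocol uses the same verb for deaths in remission and for subjects simply without a reported relapse, so it separates the two by date and not by status. In the RFS, EFS and OS rules just above, censoring has its ordinary meaning, and a programmer could carry that meaning down. Taken literally, subjects without a reported relapse also include those who died in remission, which would give them two possible end dates.

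Ordinary censoring treats a subject who died in remission as still able to relapse later, at the same rate as those who remain. The result would then answer a different question from the one the protocol names, and the error runs one way: relapse is overstated. In a leukaemia trial with intensive chemotherapy and transplantation, deaths in remission are plausible, so the point deserves a check.

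**Working it through.** **No figure to reproduce.** The documents state no cumulative incidence of relapse (CIR), relapse rate or death-in-remission rate. All rates below are assumptions.

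**Step 1: the identity.** At each event time, the Aalen-Johansen CIR adds S × d₁/n, where S is the probability of being free of both relapse and death, d₁ the number of relapses and n the number at risk. If deaths are recoded as censored, S falls only at relapses and the sum equals 1 − KM.

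Take six made-up remitters: death at month 2, relapse at 4, death at 6, relapses at 8 and 10, censored at 12.

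- Deaths as competing events: 1/6 + 1/6 + 1/6 = 0.500.
- Deaths as censored: 1 − (4/5)(2/3)(1/2) = 0.733, the same as 1 − KM.

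**Step 2: size under constant hazards.** With relapse hazard λr and death hazard λd:

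- CIR(T) = λr/(λr + λd) × [1 − exp(−(λr + λd)T)]
- Literal coding gives 1 − exp(−λr T)

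Assume λr = 0.5 per year. The 2- and 3-year horizons are borrowed from the RFS/EFS/OS paragraph; no CIR time point is stated.

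| λd per year | CIR, 2 y | Literal, 2 y | Excess (points) | CIR, 3 y | Literal, 3 y | Excess (points) |
|---|---|---|---|---|---|---|
| 0 | 63.2% | 63.2% | 0 | 77.7% | 77.7% | 0 |
| 0.1 | 58.2% | 63.2% | 5.0 | 69.6% | 77.7% | 8.1 |
| 0.25 | 51.8% | 63.2% | 11.4 | 59.6% | 77.7% | 18.0 |
| 0.5 | 43.2% | 63.2% | 20.0 | 47.5% | 77.7% | 30.2 |

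**Step 3: size at the planned Group B number.** Suppose all six subjects remit, with 2 relapses (R), 2 deaths in remission (D) and 2 subjects censored last. The CIR is 2/6 = 33.3% in every order. Literal coding gives:

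| Order | 1 − KM |
|---|---|
| RRDD | 1 − (5/6)(4/5) = 33.3% |
| RDRD | 1 − (5/6)(3/4) = 37.5% |
| DRRD | 1 − (4/5)(3/4) = 40.0% |
| RDDR | 1 − (5/6)(2/3) = 44.4% |
| DRDR | 1 − (4/5)(2/3) = 46.7% |
| DDRR | 1 − (3/4)(2/3) = 50.0% |

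The excess is 0 to 16.7 points, and zero only when no death precedes a relapse. The exact 95% CI for 2/6 runs from 4.3% to 77.7%, so either coding would be very imprecise. Six remitters is also generous: Protocol Section 1.1 cites induction CR rates of 20% to 85%, which is 6 × 0.20 = 1.2 to 6 × 0.85 = 5.1 of six.

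**Step 4: where this would enter the results.** Group B did not open. For Group A, "the synoptic CSR will only include listings for efficacy analyses". A listing shows dates and status for each subject; it forms no risk set and estimates nothing. In the visible plan, no output depends on the coding.

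**The case for a change.** The strongest case for a change is that the contradiction is real, the consequence is algebraic and not a matter of taste, and the wording would be cheap to repair. The protocol should be correct on its own terms whatever happened to enrolment. A listing of remission duration, if one is produced, would still need a status for a death in remission, and the two sentences point to different ones.

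The textual conflict and the identity stand. The rest carries less weight.

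- The literal reading empties the method sentence of meaning, because no competing event would remain. An analyst asked for a CIR with death as a competing risk would take the later sentence as the end date of the variable and code the death as a competing event.
- One cannot say that the plan is silent on status while the endpoint definitions are hidden from the public copies.
- A remission-duration listing is not visible in the SAP. If one is made, showing the date and fact of death tells the reader what happened under either label.
- Repair is not quite free. Protocol Section 9.2.1 requires ethics committee approval of modifications, here for a study already being closed. An obvious rewrite that censors only subjects known to be alive would leave those lost to follow-up unclassified.

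**Conclusion.** No change is needed. The paragraph is loosely worded, but it names the correct estimator, and a sensible reading reconciles the two sentences: the duration ends at death, and the death counts as a competing event. The potential error, 0 to 20.0 points at 2 years and 0 to 30.2 points at 3 years, rests wholly on assumed hazards. Its upper end needs death in remission to be as frequent as relapse, which nothing in the documents supports.

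The practical effect on this trial is nil as far as the documents show, because the only group enrolled has its efficacy data listed and no CIR is planned. This conclusion rests on the SAP's visible scope. If a CIR were estimated after all, deaths without relapse would have to be kept as competing events for the result to be the quantity the protocol names.

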### **Continuous Endpoints**

TTR will be summarized using descriptive statistics.

### **Categorical Endpoints**

For the analysis of Proportion of bridging to SCT, subjects who do not have evaluable post-treatment assessment to characterize response will be counted as non-responder. For this analysis, the corresponding 95% exact CIs will be provided.

## **8.6. Safety Analysis**

All safety data collected on or after the date that ENTO is first dosed up to 30 days after the permanent discontinuation of study treatment will be summarized by dose level.

### **8.6.1. Extent of Exposure**

Descriptive information will be provided by phase and dose level regarding the number of doses of study treatment prescribed the total number of doses taken, duration of treatment, and the number of prescribed dose reductions and interruptions.

ENTO compliance will be described in terms of the proportion of study treatment actually taken based on returned pill count relative to the amount that was dispensed (taking into account physician-prescribed reductions and interruptions).

